7. EFFICACY

Sample data displays are provided in [Appendix A](#).

7.1. General Considerations

Efficacy endpoints of this study are secondary and include ORR, DOR, duration of disease control, and PFS by investigator assessment based on RECIST v1.1 and mRECIST v1.1.

7.2. Efficacy Hypotheses

Each Simon 2-stage design will test the null hypothesis that the true ORR is less than or equal to the clinically insignificant response rate 5% against the alternative hypothesis that the true ORR is equal to the target ORR of 25%.

7.3. Analysis of the Primary Efficacy Parameter

Not applicable.

7.4. Analysis of the Secondary Efficacy Parameter

7.4.1. Response Criteria

Overall disease status will be categorized using RECIST v1.1 and mRECIST v1.1. Subjects will have their overall response evaluated as CR, PR, SD, PD, or NE at each postbaseline radiological assessment based on changes in target lesions, nontarget lesions, and appearance of new lesions.

7.4.2. Objective Response Rates and Best Overall Response

A subject is defined as an objective responder if the subject has an overall response of CR or PR at any postbaseline visit before first PD. Objective responders will be assessed based on both RECIST v1.1 and mRECIST v1.1.

Objective response rate is defined as the proportion of subjects with objective responses. Objective response rate will be estimated with 95% CIs overall by cohort-specific tumor type. Confidence intervals will be calculated based on the method for Simon 2-stage CIs of response rates outlined in Koyama and Chen ([Koyama and Chen 2008](#)). Subjects who do not have sufficient baseline or on-study response assessment information to be adequately assessed for response status will be included in the denominators in the calculation of ORR.

7.4.2.1. Objective Response Rate by RECIST v1.1

Under RECIST v1.1, the best overall response is determined on subject level using the highest overall response achieved postbaseline before and including the first PD, in the order of CR, PR, SD, PD, and NE. Responses of CR, PR, or SD after the first assessment of PD will not be considered. In the case of SD, measurements must meet the SD criteria at least after the date of first dose at a minimum of 49 (56-57) days. Subjects who fail to meet this criterion will have best overall response of PD if the next available assessment indicated PD or NE if there is no additional assessment available.

For subjects with measurable disease at baseline, the RECIST v1.1 assessment criteria presented in [Table 3](#) can be used to determine the overall disease status at a given timepoint based on the target lesion, nontarget lesion, and new lesion assessment.

Table 3: RECIST Evaluation Criteria for Overall Response: Measurable Disease at Baseline

Target Lesions	Nontarget Lesions	New Lesions	Overall Response
CR	CR	No	CR
CR	Non-CR/non-PD	No	PR
CR	NE	No	PR
PR	Non-PD or NE	No	PR
SD	Non-PD or NE	No	SD
Not all evaluated	Non-PD	No	NE
PD	Any	Yes or No	PD
Any	PD	Yes or No	PD
Any	Any	Yes	PD

7.4.2.2. Objective Response Rate by mRECIST v1.1

The mRECIST v1.1 instrument was adapted from RECIST v1.1 to include criteria that accounts for new lesions that can occur in immuno-oncology subjects before the occurrence of an SD, PR, or CR. Under mRECIST v1.1, if radiologic imaging shows PD, tumor assessment should be

repeated at a minimum of 4 weeks but not more than 6 weeks later to confirm the progression. If there is no second PD tumor assessment in the 4- to 6-week follow-up time, the PD will be defined as unconfirmed. [Table 4](#) lists the scenarios that can occur after an unconfirmed PD in at least 4 weeks and no more than 6 weeks, and provides rules for determining whether or not the unconfirmed PD will be counted as an event in the corresponding scenario.

Table 4: Rules for Determining PD Event Status After an Unconfirmed PD

Event Occurring After Unconfirmed PD in the Confirmation Window (4-6 Weeks)	PD Event Status
Subject had EOS/EOT or started new anticancer therapy.	PD will be confirmed as a PD.
Subject had a confirmed PD.	PD will be confirmed as a PD.
Subject had an CR, PR, SD, or NE.	PD will not be considered as a PD and counted as corresponding CR, PR, SD, or NE for the second timepoint only.

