Regular telephone conferences with study investigators will be scheduled by the sponsor in order to review cohort-specific data and overall safety data, agree on dose escalation, adjudicate individual high-grade AEs as potentially dose-limiting, and guide other major study decisions.

Efficacy Assessments:

Disease assessments will be performed based on RECIST v1.1 and also on mRECIST to account for the unique tumor response characteristics seen with immunotherapy. Modified RECIST will be defined as RECIST v1.1 with required confirmation of disease progression in the absence of clinical deterioration. The best overall response for subjects will be defined as the best overall response occurring during treatment, even if this assessment occurs after an initial assessment of progressive disease.

Assessment of tumor size (by magnetic resonance imaging or computed tomography scan) will be performed at screening or baseline (before beginning therapy) and every 8 weeks for 12 months and then every 12 weeks thereafter until disease progression is determined. Disease progression is defined as progression confirmed by a second consecutive assessment at least 4 weeks but no later than 6 weeks apart with the option for continuing treatment while awaiting radiographic confirmation of progression where feasible, provided that the subject meets the following definition of clinical stability:

- Absence of clinically significant signs and symptoms (including worsening of laboratory values) indicating disease progression.
- No decline in ECOG performance status.
- Absence of rapid progression of disease.
- Absence of progressive tumors at critical anatomical sites (eg, cord compression) requiring urgent alternative medical intervention.

Subjects who discontinue study drug for a reason other than disease progression will continue to be assessed for their disease status during the follow-up phase and should continue to have tumor assessments every 8 weeks for the first 12 months and then every 12 weeks thereafter until a new cancer therapy is started, disease progression, death, or the end of the study, whichever occurs first.

Pharmacokinetic Assessments:

Serum PK samples will be obtained at Cycle 1 (Day 1, Day 2, and Day 7), Cycle 2 Day 1, Cycle 3 Day 1, Cycle 4 Day 1, Cycle 6 (Day 1, Day 2, and Day 7), and Cycle 7 Day 1. [REDACTED]

[REDACTED] Adjustments to the timing of blood sample

collection after dose administration may be made based on emerging PK data.

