As noted above, if disease progression is observed, then the study site may elect to continue treatment; repeat imaging at a minimum of 4 weeks, but no later than 6 weeks later; and assess tumor response or confirmed progression per mRECIST.

In determining whether or not the tumor burden has increased or decreased, study site investigators should consider all target lesions as well as nontarget lesions. Subjects that are deemed clinically unstable are not required to have repeat tumor imaging for confirmation. If radiologic progression is confirmed by subsequent scan, then the subject should be discontinued from study treatment. If radiologic progression is not confirmed, then the subject should resume or continue study treatment and have the next tumor imaging according to the Protocol schedule (see Table 7). If progression is not confirmed and the subject continues on treatment, then the next scan that documents disease progression (and is confirmed by a second scan at least 4 weeks but no later than 6 weeks later) will be considered the date of disease progression.

If a subject has confirmed radiographic progression (ie, 2 scans at least 4 weeks, but no later than 6 weeks apart demonstrating progression) per mRECIST, but the subject is achieving a clinically meaningful benefit, an exception to continue treatment may be considered after consultation with the medical monitor. Clinically stable subjects at the confirmatory scan should also have no further increase in the target lesions, no unequivocal increase in nontarget lesions, and no additional new lesions develop (nonworsening disease progression) to continue study treatment.

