7.4.8.2. Progression-Free Survival by mRECIST v1.1

Under mRECIST v1.1, PFS is defined as the length of time between the baseline visit (Day 1) and the earlier of death or first overall confirmed assessment of PD (as described in [Section 7.4.2.2](#)).

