7.4.8.2.1. Confirmation of Progression per mRECIST v1.1

Under mRECIST v1.1, the assessment of PD will be confirmed by a second consecutive assessment at least 4 weeks but no later than 6 weeks apart with the option for continuing treatment while awaiting radiologic confirmation of progression ([Table 4](#)).

- If after the first unconfirmed PD, there is an EOT/EOS or a new treatment is started, this unconfirmed PD will be counted as a confirmed PD, and DOR will be defined as the time from the first overall response (CR or PR) to this PD, or death from any cause if occurring sooner than the PD.
- If a second PD occurs after the first unconfirmed PD, the first unconfirmed PD will be counted as a confirmed PD, and DOR will be defined as the time from the first overall response (CR or PR) to the first PD, or death from any cause if occurring sooner than the confirmed PD.
- If a CR, PR, SD, or NE occurs after the first unconfirmed PD, the unconfirmed PD will not be counted as a PD. If there is no further PD assessment, DOR will be censored.

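### SAP Table 4 applies the 4-to-6-week window to treatment stop and new therapy but SAP 7.4.8.2.1 does not, so mRECIST event status is contradictory for subjects who stop at first PD

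*SAP*

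**What the plan says.** **SAP 7.4.2.2 and Table 4.** The section sets the default: "If there is no second PD tumor assessment in the 4- to 6-week follow-up time, the PD will be defined as unconfirmed". The sentence that introduces Table 4 repeats the window, and the column heading reads "Event Occurring After Unconfirmed PD in the Confirmation Window (4-6 Weeks". One row under that heading is "Subject had EOS/EOT or started new anticancer therapy", and its result is that the PD counts. The other rows are a confirmed PD (counts) and a CR, PR, SD or NE (does not count).

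**Where that rule is used.** SAP 7.4.8.2 ends mRECIST PFS at "the earlier of death or first overall confirmed assessment of PD" and points to 7.4.2.2 for what confirmed means. SAP 7.4.4.2 (duration of response, DOR) and 7.4.5 (duration of disease control) also take their PD criteria from 7.4.2.2.

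**SAP 7.4.8.2.1.** The lead-in gives the 4-to-6-week interval for a second PD and cites Table 4. The bullet on stopping has no interval: "If after the first unconfirmed PD, there is an EOT/EOS or a new treatment is started, this unconfirmed PD will be counted" as confirmed. Footnote [1] of shell Tables 2.2.1 and 2.2.2 in SAP Appendix A says the same, again with no interval.

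**SAP Table 5.** Subjects with no progression, subjects who discontinue, and subjects who start new anticancer treatment are censored at the last valid scan. SAP 7.4.4 applies the same censoring to DOR.

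**Protocol.** The Synopsis states: "Modified RECIST will be defined as RECIST v1.1 with required confirmation of disease progression in the absence of clinical deterioration". Protocol 7.7.1 adds: "Subjects that are deemed clinically unstable are not required to have repeat tumor imaging for confirmation". Protocol Table 12 takes clinically unstable subjects off treatment at the first PD and leaves the repeat scan to the physician.

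**The concern.** Two parts of one SAP give different event status to the same subject, and the subject is a common one: PD on a scan, drug stopped, no repeat scan. If the windowed version is programmed, a documented progression becomes a censored time.

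The clinically unstable are the clearest case, because the Protocol sends them off drug at once. Censoring them is informative: Kaplan-Meier would assume that they go on to progress at the same rate as those still under observation, when they have already progressed. Follow-up would not reliably restore the event. Protocol 6.4.2 continues disease follow-up only for subjects who stop for reasons other than progression, and the planned safety visits end 60 days (+7) after EOT. The trial is open-label, so the choice should not be left to programming after data are seen.

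**Working it through.** The plan states no figure on this point, so there is none to reproduce. The check is a comparison of rules, a timing check and an illustration of size.

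**1. Rules side by side**

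| Event after a first, unconfirmed PD | SAP 7.4.2.2 and Table 4 | SAP 7.4.8.2.1 | Shell footnotes | Protocol |
|---|---|---|---|---|
| EOT/EOS or new therapy in Weeks 4 to 6 | event | event | event | no rule for stable subjects; confirmation not required if deteriorating |
| EOT/EOS or new therapy before Week 4 or after Week 6 | no row | event | event | as above |
| Second PD | Weeks 4 to 6 | Weeks 4 to 6 (lead-in) | 4 to 6 weeks, where possible | Weeks 4 to 6 |

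The disagreement is in the second line only.

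**2. Timing**

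- The window is 4 × 7 = 28 to 6 × 7 = 42 days after the PD scan.
- The EOT visit has a window of ±3 days (Protocol Table 7). If drug is stopped when the PD is found, EOT falls within days of the scan, well before day 28.
- Scheduled scans are 56 days apart, each ±7 days. The next one therefore falls 56 − 14 = 42 to 56 + 14 = 70 days after the PD scan, and only the extreme of 42 touches the window. Without an extra scan, the repeat-scan rows do not usually apply either.

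**3. One subject traced through**

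Take a clinically unstable subject with PD on the first scan, EOT 3 days later and no repeat scan.

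- *Table 4, literally:* EOT at day 3 is outside days 28 to 42, so no row applies. The PD stays unconfirmed and is not a PFS event under 7.4.8.2. The nearest Table 5 rows censor at the last valid scan, which is the PD scan.
- *SAP 7.4.8.2.1 and the shell footnotes:* the PD is an event.
- *Protocol definition:* confirmation is not required, so the PD stands.

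If this subject then starts new therapy, the new-treatment row of Table 5 also censors at the PD scan. It does not say whether it yields to an earlier PD.

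**4. Size, under assumed inputs**

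Let f be the share of first PDs followed by a drug stop before Week 4. Neither f nor the hazard is in the documents. Assume that all events are PD and that the f subjects are a random share. Censoring them at the PD date reduces the apparent hazard to (1 − f) times the true one.

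- *Exponential PFS:* the median is multiplied by 1/(1 − f), which is 1/0.8 = 1.25 at 20%, 1/0.7 = 1.43 at 30% and 1/0.5 = 2 at 50%.
- *8-week scans, first-PD probability q per scan:* S after k scans = (1 − q(1 − f))^k. The median is the first scan with S ≤ 0.5, and Week 24 is k = 3.

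| q | f | Median (weeks) | Week-24 PFS |
|---|---|---|---|
| 0.5 | 0 | 8 | 0.5³ = 12.5% |
| 0.5 | 25% | 16 | 0.625³ = 24.4% |
| 0.5 | 50% | 24 | 0.75³ = 42.2% |
| 0.5 | 75% | 48 | 0.875³ = 67.0% |
| 0.3 | 0 | 16 | 0.7³ = 34.3% |
| 0.3 | 25% | 24 | 0.775³ = 46.5% |
| 0.3 | 50% | 40 | 0.85³ = 61.4% |
| 0.3 | 75% | 72 | 0.925³ = 79.1% |

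The f = 0 rows are what SAP 7.4.8.2.1 would give. Over f = 25% to 75% the median is multiplied by 24/16 = 1.5 up to 48/8 = 6. The medians move in 8-week steps, so the Week-24 column is the smoother guide.

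**The case against.** No SAP sentence says that a subject who stops at first PD is censored. Section 7.4.8.2.1, which sits inside the PFS section, and two shell footnotes make that subject an event. The Table 4 heading might be read as status by the time of the window, so that a subject already off drug has had EOT. Table 5 has no row for a documented but unconfirmed PD followed by discontinuation. All of this stands, and it makes the censoring a consequence of one reading. It does not settle which reading governs, because 7.4.8.2 sends the reader to 7.4.2.2, and 7.4.8.2.1 itself cites Table 4.

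The consequence is also limited. These are secondary endpoints, SAP 3.3 calls all analyses exploratory, no decision rule uses PFS or DOR, and the RECIST v1.1 versions count the first PD and are unaffected. The illustration ignores deaths, which are PFS events and are likely in deteriorating subjects. It therefore shows a direction and a range and does not forecast the bias.

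Three stronger readings are tempting, and the documents do not support them:

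- *That the window on a second PD is also wrong.* The Protocol sets that window itself, and the 7.4.8.2.1 lead-in repeats it.
- *That the Protocol is contradicted for everyone who stops at first PD.* It waives confirmation only where there is clinical deterioration. For stable subjects who stop without a repeat scan it requires confirmation and gives no counting rule.
- *That the Part 2 Simon response count changes.* SAP Section 9 states its own 4-to-6-week rule for a CR or PR after an unconfirmed PD, and mRECIST best response runs to the first confirmed PD. A later response could therefore still count, and no effect on the Stage 1 decision is established.

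**Conclusion.** The concern holds as an internal contradiction over the timing of EOT/EOS and new therapy. If Table 4 is followed literally, subjects who stop drug at first PD lose their mRECIST event. For the clinically unstable among them, that contradicts the Protocol. The resulting bias in PFS, DOR and duration of disease control would be upward. For duration of disease control this assumes the same censoring as PFS, since SAP 7.4.5 states none.

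The size cannot be fixed from the documents. It grows as 1/(1 − f) under a constant hazard, for an unknown f, and deaths would change it. Because the endpoints are secondary and the RECIST v1.1 analyses run in parallel, this is a point to correct before analysis and does not threaten the trial's main conclusions.

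**What to change.** 1. In SAP Table 4, limit the 4-to-6-week heading to the repeat-scan rows, and make the introducing sentence match.
2. State one rule: a first PD with clinical deterioration, or followed by EOT/EOS or new anticancer therapy at any time before a later non-PD scan, is an event dated at that first PD.
3. Make SAP 7.4.8.2.1 and Table 5, including its new-anticancer-treatment row, refer to this rule and not restate it.
4. Keep the Protocol's 4-to-6-week window for a second PD. How to count a repeat scan outside that window needs an explicit sponsor decision, because accepting one would depart from the Protocol's definition.

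The cost is SAP wording and programming. mRECIST PFS and DOR may come out somewhat shorter than under literal Table 4. No visit, scan or treatment rule changes.

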7.4.3. Subgroup Analyses of Objective Response Rates

Subgroups will be formed based on the following subject characteristics and baseline variables for those subjects whose data are available.

- PD-L1 expression within tumor type: high versus negative/low
- Prior treatment with an anti-PD-1/PD-L1 therapy within tumor type: Yes/No
- Number of prior therapies for advanced and metastatic disease within tumor type
- Subjects with > 1 postbaseline scan within tumor type
- Tumor-type disease characteristics including the following:
 - Endometrium – MSI status (high, low, stable, unknown)
 - Ovarian – Histology and BRCA status
 - Melanoma – BRAF mutation status (mutated, wild-type, unknown), PD-L1 status (positive or negative)
 - NSCLC – Histology (squamous or nonsquamous), PD-L1 status (positive or negative)
 - RCC – MSKCC score (Poor, Intermediate, Good), PD-L1 status (positive or negative)

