7.7.1.1.2. Tumor Imaging During the Study

The first imaging assessment should be performed 8 weeks after the first dose of study drug, every 8 weeks (56 days \pm 7 days) for 12 months, and then every 12 weeks (84 days \pm 7 days) thereafter until disease progression is determined. Imaging assessments may be performed more frequently if clinically indicated. **Imaging should not be adjusted for delays in cycle starts.**

Per mRECIST v1.1, response should be confirmed by a repeat radiographic assessment not less than 4 weeks from the date that the response was first documented. The scan for confirmation of response may be performed at the earliest of 4 weeks after the first indication of response or at the next scheduled scan, whichever is clinically indicated.

Imaging should continue to be performed until documented disease progression, the start of new anticancer treatment, withdrawal of consent, death, or the end of the study, whichever occurs first. Disease progression should be confirmed at least 4 weeks, but no later than 6 weeks after the first scan indicating progression in clinically stable subjects. Subjects who have unconfirmed disease progression may continue on treatment until progression is confirmed, provided that they have met the conditions detailed in [Section 7.7.1](#). A central imaging vendor will not be used in this study.

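### One ORR subgroup is defined by a post-treatment condition (a second postbaseline scan), so its response rate is very likely biased upward

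*SAP*

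**What the plan says.** SAP 7.4.3 opens with "Subgroups will be formed based on the following subject characteristics and baseline variables". Most of its list fits that description: PD-L1 expression, prior anti-PD-1/PD-L1 therapy, number of prior regimens, and tumor-specific markers. One entry does not: "Subjects with > 1 postbaseline scan within tumor type". The section gives it no rationale, comparison group, landmark time or caveat.

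The passages that decide who ends up in this subgroup are these:

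- **Timing.** Protocol 7.7.1.1.2: "The first imaging assessment should be performed 8 weeks after the first dose of study drug", then every 8 weeks for the first 12 months.
- **After a scan showing progression.** Clinically stable subjects are due a repeat scan 4 to 6 weeks later (Protocol 7.7.1 and 7.7.1.1.2). For the others, Protocol 7.7.1 says "Subjects that are deemed clinically unstable are not required to have repeat tumor imaging for confirmation".
- **Main ORR denominator.** SAP 7.4.2 keeps in subjects whose assessments are inadequate: those who cannot be assessed for "response status will be included in the denominators in the calculation of ORR".
- **Who is a responder.** SAP 7.4.2 counts anyone who "has an overall response of CR or PR at any postbaseline visit before first PD". Protocol 7.7.1.1.2 adds that under mRECIST "response should be confirmed by a repeat radiographic assessment not less than 4 weeks from the date that the response was first documented", and SAP 9 repeats this.

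**The concern.** The number of scans a subject has had is not a baseline characteristic. It depends partly on how the subject fared. With the first scan at Week 8, someone who dies or drops out before a second scan cannot enter the subgroup, and neither can someone who progresses while clinically unstable and is not scanned again. These are nearly all nonresponders. Taking them out of the denominator while the responders stay raises the response rate without any change in the drug's activity.

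This undoes, in one prespecified analysis, the protection that SAP 7.4.2 gives the main ORR. What is at stake is interpretation. A tumor-type ORR from this subgroup could be read against the 5% and 25% benchmarks in SAP 7.2, which were set for the whole cohort. With at most 17 subjects per cohort, a few exclusions move the figure visibly.

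**Working it through.** **The plan's own figures.** The SAP gives no number for this subgroup. Its design figures reproduce. With n1 = 9, n2 = 8, stop at 0 of 9 and nonpromising at 2 or fewer of 17:

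- The rejection probability is the sum over x = 1 to 9 of P(X1 = x) × P(X2 ≥ 3 − x). This gives 0.0466 at a 5% response rate (limit 0.05) and 0.812 at 25% (stated power 80%).
- Early termination is (1 − p)^9, giving 23.2%, 13.4%, 7.5%, 4.0% and 2.1% at 15%, 20%, 25%, 30% and 35%. All match SAP Table 8.

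**Who is left out.** Let f be the share of subjects with 0 or 1 postbaseline scan.

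- No scan: cannot be a responder.
- One scan showing progression, stable disease or a non-evaluable result: not a responder.
- One scan showing CR or PR: a responder under SAP 7.4.2, but not if the response must be confirmed, because confirmation needs a second scan.
- Clinically stable with progression at Week 8: due another scan at about Weeks 12 to 14 (8 + 4 to 8 + 6), so normally kept in as a nonresponder.

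**Formula.** Subgroup ORR = (ORR_all − f × ORR_excluded) / (1 − f). It exceeds ORR_all exactly when ORR_excluded is below ORR_all. If response must be confirmed, ORR_excluded = 0 and the inflation factor is 1/(1 − f), that is N/n, with n the number in the subgroup.

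**Size.** The documents do not give f. Assuming 10% to 50%, with all excluded subjects nonresponders:

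| f | true 5% reads | true 25% reads |
|---|---|---|
| 10% | 0.05/0.9 = 5.6% | 0.25/0.9 = 27.8% |
| 20% | 6.3% | 31.3% |
| 30% | 7.1% | 35.7% |
| 40% | 8.3% | 41.7% |
| 50% | 10.0% | 50.0% |

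In a full cohort of 17, again excluding only nonresponders:

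- 3/17 = 17.6% reads 3/15 = 20.0% with 2 excluded, 3/12 = 25.0% with 5, and 3/10 = 30.0% with 7.
- 2/17 = 11.8% reads 2/12 = 16.7% with 5 excluded and 2/9 = 22.2% with 8.

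**If one-scan responders count.** With ORR_all = 25% and ORR_excluded = 5%, the subgroup reads (0.25 − 0.2 × 0.05)/0.8 = 30.0% at f = 20% and (0.25 − 0.4 × 0.05)/0.6 = 38.3% at f = 40%. The shift can reverse in a small cohort: if the 5 excluded from a 3/17 cohort include one one-scan responder, the subgroup reads 2/12 = 16.7%, below 17.6%.

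**The case against.** The strongest reply is that the documents already limit the damage.

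- **Second scans are not confined to subjects who are doing well.** Stable progressors are due one. Subjects who stop without confirmed progression should be imaged at discontinuation unless scanned in the preceding 4 weeks (Protocol Table 7, footnotes). Those who stop for other reasons stay on the imaging schedule until progression, new therapy, consent withdrawal, death or study end (Protocol 6.4.2 and 7.7.1.1.3). This stands. A reader might infer that the subgroup removes early progressors in general, and the imaging rules do not support that. The excluded share may also be small.
- **The direction is not guaranteed.** This stands too. A reader might infer inflation by construction in every tumor type. Under the single-visit definition that is very likely but not certain, as the 2/12 example shows.
- **No decision depends on it.** A reader might infer that the subgroup could turn a failing cohort into a passing one. The Simon rule counts responders, and narrowing the denominator adds none. SAP 5.3.3 names the Part 2 FAS tumor-type groups for that rule. If the rule were run on 9 and then 17 such selected subjects, rejection at a true overall 5% would rise from 0.047 to 0.080 (f = 20%) or 0.153 (f = 40%), but nothing in the SAP does this.
- **No planned table shows it.** The Appendix A efficacy tables list no subgroup ORR, so how prominently the figure would appear is unknown.
- **The view has a purpose.** Stage 1 futility is judged at Week 16 with at least 2 scans (SAP 9), so looking at subjects with enough imaging to confirm response is understandable. This supports relabelling as an alternative to deletion, but not keeping the entry among baseline subgroups.

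SAP 3.3 calls all analyses exploratory. That bears on error control and does not correct a biased estimate.

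**Conclusion.** The point holds within limits. SAP 7.4.3 prespecifies a subgroup that contradicts the section's own description and selects subjects on what happened after treatment began. Its ORR is very likely biased upward. If response must be confirmed it cannot be biased downward, and the factor is N/n.

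The size rests on two assumptions: an excluded share that the documents do not state, and no responders among those excluded. Over an assumed 10% to 50%, a 25% ORR is overstated by 2.8 to 25 percentage points. The effect is confined to this one exploratory estimate.

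**What to change.** Either of two changes to SAP 7.4.3 resolves it:

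1. Delete the entry. Beside the FAS ORR for each tumor type, report how many subjects had no second postbaseline scan, by reason (death, clinically unstable progression, withdrawal, new therapy, other).
2. If the view is wanted, move it out of the baseline subgroups and label it a response-evaluable sensitivity analysis, always presented with the FAS ORR and the exclusions by reason.

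While editing, state what evaluable means in SAP 3.4.2 and 9, so that it is not taken to mean more than one scan.

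The cost is one line removed or relocated and a short count per cohort from data already collected. No change to sample size, visits or decision rules is needed.
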